3.0 Study Endpoints/Events/Outcomes

- 3.1 Primary Endpoint/Event/Outcome: The primary outcome of this research is participant satisfaction as measured by:
 - Client Satisfaction Questionnaire-8 at week 8.
- 3.2 Secondary Endpoint(s)/Event(s)/Outcome(s): The secondary outcomes of this research focus on feasibility metrics and within-person change in behavioral outcomes.
 - Safety measured by documentation of treatment-related serious (e.g. injurious) and non-serious (e.g. fall without injury) adverse events that occur during the intervention period (weeks 2 through 7).
 - Enacted behavioral treatment dose measured by documentation of intervention session attendance (weeks 2 through 7).
 - Participation restrictions measured using the Activity Card Sort 3 (week 8).
 - Health-related quality of life measured using the EuroQoL-5 Dimension-5 Level (week 8).
 - Sedentary minutes measured using the activPAL micro3 monitor following an 8-day wear protocol (week 8).

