4.2 Drug/Device Handling: N/A

4.3 Biosafety: N/A

4.4 Stem Cells: N/A

4.5 Fetal Tissue: N/A

5.0 Procedures Involved

- 5.1 Study Design: This study uses a sequential case series design to refine the intervention and study protocol based on feedback from participants and the treating therapists. Participants will complete assessments at Baseline (week 1) and 2-months (week 8), participate in 12 intervention sessions over 6 weeks (weeks 2 through 7), and complete 2 interviews (mid-intervention and week 8). Participants will also wear an activPAL activity monitor for 8 days at baseline and 2-months to assess sedentary behavior.
- 5.2 Study Procedures: Participants will be recruited through Courage Kenny Rehabilitation Institute, community-based recruitment, and Fairview Health System (see section 11.1 to 11.3). Interested potential participants will complete a screening questionnaire over the telephone (see section 8.3). Those deemed eligible will meet with study staff to review the informed consent document and have an opportunity to ask questions before deciding whether they want to consent to participate in the study. Participants who choose to provide consent

Page 9 of 44

Template Revised On: 10/28/2022

VERSION DATE: 07.21.2023

will complete eConsent (see section 21.1). After providing consent, the participant will be scheduled to complete the baseline testing session. The schedule of measures is depicted in Table 3. All study procedures, including assessments and intervention sessions, will be conducted remotely using videoconferencing (HIPAA-compliant University of Minnesota Health Care Component Zoom). The study staff administering each questionnaire will display the questions and response options on the Zoom screen. In addition, study staff may read the questions aloud if the participant prefers. The participant will provide a verbal response for all measures. All procedures will be conducted for research purposes.

Table 3: Schedule of Measures

W1	W2	W3	W4	W5	W6	W7	W8
Χ							
Χ							Х
	Χ						X X X
Χ							X
Χ							Χ
Χ							Χ
Χ							X
Χ							Χ
Χ							
Χ							
							Χ
Χ							
Χ							
Χ							
Χ							
Χ							Χ
	X X X	X	X	X	X	X	X X X X X X X X X X X X X X X X X X X

NCT05029284

VERSION DATE: 07.21.2023

Unsupervised blood pressure (3	Χ		X
min/day for 7 days)			
activPAL 8-day monitoring (10	Χ		X
min instruction, 2 min/day)			
Interview 1 (30 min)		Χ	
Interview 2 (30 min)			X

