- Interview 1: This interview will be conducted within 14 days after session 5 and focus on the participants' perspectives on: 1) learning to use videoconferencing in the context of the teleABLE intervention, 2) accessing videoconferencing, and 3) ways that the therapist and/or support person support their use of videoconferencing during the study. The interview will be conducted by a research assistant supervised by the PI. We anticipate that the interview will last 30 to 60 minutes. Interviews will be audio recorded using the Zoom record function. The resulting audio file will be stored in the study's UMN BOX folder. Interviews will be transcribed by a company called Research Transcriptions (previously SameDayTranscriptions). Research Transcriptions provides confidential transcription services, using HIPAA-compliant procedures. Interviews will be transcribed in batches based on data accumulation. Deidentified transcripts will be stored in the study's UMN BOX folder.
- Interview 2: This interview will be conducted during the post-intervention assessment session after study measures are completed and will focus on participants' perspectives on the intervention, study recruitment, assessment, and intervention procedures that may enhance retention in future trials. Interviews will be audio recorded using the Zoom record function. The resulting audio file will be stored in the study's UMN BOX folder. Interviews will be transcribed by a company called Research Transcriptions (previously SameDayTranscriptions). Research Transcriptions provides confidential transcription services, using HIPAA-compliant procedures. Interviews will be transcribed in batches based on data accumulation. Deidentified transcripts will be stored in the study's UMN BOX folder.
- 5.3 Study Duration: Individual participants' study participation will occur over 8 weeks. Assessment sessions will occur during weeks 1 and 8 (2 hours per session). During the 8-day monitor wear that occurs during weeks 1 and 8, participants may spend up to 5 minutes daily completing the activPAL diary worksheet. Intervention sessions 1 and 3 through 12 will last 30 minutes each. Intervention session 2 will last 60 minutes. Interview 1, which occurs during week 5, will last 30 minutes.

We anticipate the participants will be recruited and complete all study procedures over 10 months. Data analysis will require an additional 4 months after all data are collected.

- 5.4 Use of radiation: N/A

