18.0 Provisions to Monitor the Data to Ensure the Safety of Participants

- 18.1 Data Integrity Monitoring. Data integrity will be monitored by the PI, who has over 10 years of experience working with people with stroke-related disability in clinical (as an occupational therapist) and research settings. The following strategies will be applied:
 - 1. The study team will notify the PI of new study enrollments and the PI will review the screening documentation form within 2 business days to confirm eligibility to proceed with the informed consent meeting.

Page 34 of 44

VERSION DATE: 07.21.2023

- 2. Procedural checklists will be reviewed for completeness following each study visit by the study staff responsible for each visit. Reasons for missing data will be documented in REDCap.
- 3. The PI will hold weekly meetings with the study team to review study enrollment, monitor volunteer progression through study procedures, review case report forms, and monitor adverse events. Meetings will be documented and meeting minutes will be stored electronically with the study files in the University of Minnesota Box Secure Storage.
- 18.2 Data Safety Monitoring. This study will be overseen by a data safety monitor external to the trial and institution who has expertise in neurorehabilitation trials. The PI will meet with the data safety monitor every 6 months to review a report that includes: participant accrual, adverse events data, and data completeness. Adverse events data will be collected at two timepoints during the study: (1) during the interview 1 session, and (2) during post-intervention assessments. Data will be collected over the telephone or Zoom using a questionnaire. Ad hoc reports of adverse events will also be collected by any study staff who become aware of an adverse event during any study interaction. Whomever first identifies the adverse event will complete an ad hoc form and notify the PI who will determine appropriate follow-up actions and reporting.

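### Adverse events are scheduled to be asked about only at Interview 1 and at week 8, with unscripted ad hoc reporting in between, so non-serious events may be under-counted

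*Combined protocol and SAP*

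**What the plan says.** **Collection.** Section 18.2 schedules a questionnaire, given by telephone or Zoom: "Adverse events data will be collected at two timepoints during the study: (1) during the interview 1 session, and (2) during post-intervention assessments". It then adds a second route: "Ad hoc reports of adverse events will also be collected by any study staff who become aware of an adverse event". That route applies at any contact with the participant, uses an ad hoc form and requires the PI to be told. Under section 18.1, weekly team meetings "review case report forms, and monitor adverse events".

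**Endpoint and benchmark.** Section 3.2 lists as a secondary outcome "Safety measured by documentation of treatment-related serious (e.g. injurious) and non-serious (e.g. fall without injury) adverse events", counted over weeks 2 to 7. Section 15.3 compares the adverse event count with a benchmark of at most 1.

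**Timing.** On Interview 1, section 5.2 says: "This interview will be conducted within 14 days after session 5". Section 5.3 says: "Interview 1, which occurs during week 5, will last 30 minutes". The final assessment is in week 8.

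**Other contact.** There are 12 sessions, two a week, in weeks 2 to 7 (sections 4.1 and 5.1). Sessions 3 to 12 review the participant's ICAN Plan (Table 2), and self-assessment covers bad as well as good results of an activity (Table 1). Section 15.4 expects each session's documentation in REDCap within 48 hours.

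**The concern.** The endpoint covers six weeks and includes minor events, yet the plan schedules only two occasions on which every participant is asked about them. The route in between is passive: it works only if the participant mentions the event or the staff member notices it. A fall without injury is an event that a participant may think too trivial to volunteer and may not recall weeks later. Plan review and self-assessment at the sessions deal with planned activities and are not described as a question about all falls and injuries since the last contact. The 48-hour notes and the weekly meetings can review only what has been elicited.

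With a benchmark of at most 1 event, a single unrecorded event can change whether the benchmark is met, and under-recording pushes only towards meeting it. Late discovery would also delay the PI's review of an event linked to a planned activity. In addition, section 12.2 ends data collection at full withdrawal, so someone who withdraws fully before Interview 1 would receive neither questionnaire.

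**Working it through.** **Inputs.** Day 1 is the first day of week 1, so week *w* covers days 7(*w* − 1) + 1 to 7*w*. Week 2 is days 8–14, week 4 days 22–28, week 5 days 29–35, and week 8 days 50–56. There are two sessions a week from week 2 (sections 4.1, 5.1). Interview 1 falls 0 to 14 days after session 5 (section 5.2).

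**1. The plan's own timing of Interview 1.** If session 1 is on day *d* (8 to 14), session 5 is on day *d* + 14, that is days 22–28, in week 4. Interview 1 is then on days *d* + 14 to *d* + 28:
- earliest: 8 + 14 = day 22 (week 4)
- latest: 14 + 28 = day 42 (week 6)

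The week 5 given in section 5.3 lies inside this range.

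**2. Maximum look-back with Interview 1 in week 5.**
- At Interview 1, back to day 8: 29 − 8 = 21 to 35 − 8 = 27 days (3.0 to 3.9 weeks). A later session 1 shortens this day for day; with session 1 on day 14 it is 29 − 14 = 15 to 35 − 14 = 21 days.
- At week 8, back to Interview 1: 50 − 35 = 15 to 56 − 29 = 27 days (2.1 to 3.9 weeks).

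**3. Maximum look-back over the full interview window, from session 1.**
- Session 1 to the week 8 visit: 50 − 14 = 36 to 56 − 8 = 48 days.
- The longer of the two intervals is at least 36 / 2 = 18 days.
- It is at most 56 − 22 = 34 days. This needs session 1 on day 8, Interview 1 on the day of session 5, and the final visit on day 56.
- Range: 18 to 34 days (2.6 to 4.9 weeks).

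**4. Average recall.** Assume events spread evenly over days 8–49 (42 days), the final visit on day 53, and each event recalled at the next questionnaire. With Interview 1 on day 29, the days of recall sum to 231 + 270 = 501, and 501 / 42 = 11.9 days, or 1.7 weeks. Day 32 gives 504 / 42 = 12.0 days (1.7 weeks) and day 35 gives 525 / 42 = 12.5 days (1.8 weeks).

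**5. With a question at each session.** Two sessions a week give an average gap of 7 / 2 = 3.5 days.

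**6. Direction of bias on the benchmark (illustration only).** The documents give no event rate or capture rate. Assume a Poisson count with mean *m* = participants × true events each × proportion captured, and read the benchmark as a total across the sample. Then P(count ≤ 1) = e^(−*m*)(1 + *m*).

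| Participants | Assumed events each | 100% captured | 75% | 50% |
|---|---|---|---|---|
| 5 | 0.2 | 0.74 | 0.83 | 0.91 |
| 5 | 0.4 | 0.41 | 0.56 | 0.74 |
| 10 | 0.2 | 0.41 | 0.56 | 0.74 |
| 10 | 0.4 | 0.09 | 0.20 | 0.41 |

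For example, 10 participants at 0.2 events each give *m* = 2 and e^(−2) × 3 = 0.41. At 50% capture, *m* = 1 and e^(−1) × 2 = 0.74. In every row, lower capture makes the benchmark easier to meet.

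**The case against.** A reader might infer that the endpoint rests on recall alone. It does not. Section 18.2 provides for ad hoc reports at any contact, participants are seen twice a week, and the PI reviews adverse events weekly. Section 3.2 counts treatment-related events. A fall during a planned activity is the kind most likely to be treatment-related, and the next plan review could well bring it out.

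A reader might also infer that minor falls will be missed, or that no session asks about them. The documents support neither statement. They give no capture rate, and the session forms, the adverse event questionnaire, the Intervention Checklist, the Safety Algorithm (section 4.1) and Appendix A (section 13.1) are not in the available text. One of them may hold a prompt.

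Nor is a look-back of nearly five weeks typical: it needs Interview 1 at the edge of its window, and average recall is under two weeks on the assumptions above. Recall problems are also limited by the eligibility rules, which exclude severe cognitive impairment, dementia and diminished capacity to consent.

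Finally, the count is a secondary, descriptive outcome in a formative study of 5 to 10 people. Section 15.3 attaches no go/no-go consequence to the benchmark, and Hypothesis 1b is addressed by interviews, not by the count.

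All of this stands, and it limits the size of the problem. It does not supply a stated, systematic question between the two questionnaires. If an unseen form contains one, section 18.2 should cite it, because it now names two timepoints only.

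**Conclusion.** The point holds in a limited form. Scheduled adverse event questions occur twice, and capture between them depends on unscripted reporting. The maximum look-back is about 3 to 4 weeks at Interview 1 and 2 to 4 weeks at week 8 if Interview 1 is in week 5. Over the full window, the longer interval is 18 to 34 days. Non-serious events may be under-counted, and the bias would favour meeting the benchmark. How large the under-count would be cannot be derived from the documents.

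The plan also does not say which records (questionnaire, ad hoc form, session note) make up the count. Section 15.3 does not repeat the treatment-related restriction of section 3.2, or say whether the limit of 1 applies to the whole sample or to each participant.

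The conclusion assumes that sessions run at the planned pace and that no unseen form already contains a per-session question. It is a worthwhile, inexpensive improvement, particularly because this study exists to refine procedures for a later randomized trial. It does not show that the study is unsafe or its safety result invalid.

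**What to change.** - **Sections 18.2 and 5.2:** have the interventionist ask a short standard question on falls, injuries and medical events since the last contact at each session. Record the answer, including 'none', in the REDCap session note. If such a prompt already exists in a session form, cite it.
- **Section 18.2:** keep the questionnaires at Interview 1 and week 8 as catch-up points, and state the look-back period for each.
- **Sections 3.2 and 15.3:** state that the safety count combines session records, questionnaires and ad hoc forms, with duplicates removed.

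The cost is one or two minutes per session, a REDCap field and a small amendment, with no new visits or staff. Per-session records would also cover participants up to the point of full withdrawal. The downside is that more non-serious events will probably be recorded, so the benchmark of at most 1 becomes harder to meet.

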19.0 Provisions to Protect the Privacy Interests of Participants

19.1 Protecting Privacy: Participants' privacy will be protected throughout all interactions with the study team and in the handling of data.

Study interactions: All study visits will take place using the University of Minnesota Health Care Component Zoom portal, which is HIPAA-compliant. Participants will be encouraged to access Zoom from a private space of their choosing with no others present. If they prefer, they may use headphones to enhance privacy. Study staff will interact with participants from a private space in the School of Kinesiology or a room in their home with no other people present and a closed door (if working remotely). If not on campus, study staff will access Zoom using a private/secure internet connection. Before each assessment session and interview, participants will be reminded that they are not required to answer the questions posed, and that they may tell the study staff that they do not wish to answer particular question/s at any time during the session.

Data handling: All data collected from participants will be entered into the study database, approved web applications (REDCap, BrightOutcome), or saved to the University of Minnesota Secure BOX storage using university-owned computers. Data will be stored using the study ID code rather than participants' names. Only study staff who require access to the data to complete their study-related tasks will be granted access to the data.

Page 35 of 44

VERSION DATE: 07.21.2023

19.2 Access to Participants: All data will be provided to the research team by the study participants. Participants will be fully informed of the ways in which their data will/may be used during the informed consent process. The research team has been trained in conducting these conversations and the participants are also assessed for their understanding of consent prior to initiating any study procedures.

20.0 Compensation for Research-Related Injury

20.1 Compensation for Research-Related Injury: In the event that research-related activities result in an injury, treatment will be provided to the participant (e.g., first aid, emergency treatment, and follow-up care as needed). Care for such injuries will be billed in the ordinary manner to the participant or the participant's insurance company.

20.2 Contract Language: N/A

21.0 Consent Process

- 21.1 Consent Process (when consent will be obtained): Informed consent will occur in a phased manner throughout (1) telephone screening, and (2) study enrollment, (3) ongoing consent.
 - 1. Telephone screening: Participants who contact the DWELL Laboratory to express interest in participating in the study will provide verbal informed consent prior to completing the screening questions. Consent to complete telephone screening will be obtained by study staff who are trained and supervised by the PI. During the telephone screening call, participants will receive general information on the study procedures, detailed information on the telephone screening process, including their right to decide not to participate, and be informed of the risks associated with completing the telephone interview (i.e., breach of confidentiality, mild distress related to questions). Screening questions will be asked only after the potential participant has received this information, been offered an opportunity to ask questions, and verbally indicated that they would like to complete the telephone screening process. We are requesting a waiver of documentation of informed consent for this screening process (see below).
 - 2. Study enrollment: Participants who are deemed eligible to participate in the study based on the telephone screening will be scheduled for a Zoom meeting with a study staff member who is trained and supervised by the PI. The potential participant will be encouraged to invite a support person to this meeting, and to join the meeting from a location where they will be comfortable discussing their possible participation in the study. Prior to the meeting, a blank copy of the

Page 36 of 44

Template Revised On: 10/28/2022

NCT05029284

VERSION DATE: 07.21.2023

consent form will be sent to the potential participant in either hard copy or electronic format (based on the potential participant's preference). This form will contain the combined HIPAA Authorization/Consent document (HRP-593). During this meeting, the study staff member will review the informed consent document and provide opportunities for the potential participant and their support person to ask questions. Questions will be actively invited, and once all questions have been answered, the study staff will provide time for the potential participant and their support person to discuss their decision without study staff present (i.e. Zoom camera and microphone muted). If the potential participant decides to provide informed consent, the study staff will ask the potential participant 3 teach-back questions: (1) what are they being asked to do if they agree to participate in the study, (2) what risks are associated with the study, and (3) if they decide they no longer wish to participate in the study, how would they go about withdrawing. After the potential participant has responded to these questions accurately, the study staff will send a survey link to the eConsent form to allow the potential participant to sign electronically via REDCap.

- 3. Ongoing consent: At the beginning of each study visit, the study staff who are leading the visit will explain the purpose of the visit, the estimated time that the visit will require, and obtain verbal affirmation/permission from participant regarding their willingness to complete the study visit
- 21.2 Waiver or Alteration of Consent Process (when consent will not be obtained): N/A
- 21.3 Waiver of Written/Signed Documentation of Consent (when written/signed consent will not be obtained):

We are requesting a waiver of written informed consent to screen interested potential participants over the telephone. The telephone screening poses no more than minimal risk. Participants will respond to questions related to their age, stroke diagnosis, mobility status, daily activities, depressive symptoms, and medical comorbidities. In addition, it is impractical to ask people who have stroke-related disability to travel to the university to complete written consent for a 15-minute questionnaire for the purpose of determining their eligibility. The telephone screening will be conducted by a member of the research team supervised by [name], who is a licensed occupational therapist with 10 years of clinical and research experience directly interacting with people with stroke-related disability. During the telephone screening call, participants will receive general information on the study procedures, detailed information on the telephone screening process, including their right to decide not to participate, and be informed of the minimal risks associated with completing the telephone

NCT05029284

VERSION DATE: 07.21.2023

interview. If the participant verbally agrees to answer the screening questions, verbal consent will be documented electronically by the research assistant and the telephone screening questions will be completed.

- 21.4 Non-English Speaking Participants: N/A
- 21.5 Participants Who Are Not Yet Adults (infants, children, teenagers under 18 years of age): N/A
- 21.6 Cognitively Impaired Adults, or adults with fluctuating or diminished capacity to consent: N/A
- 21.7 Adults Unable to Consent: N/A

